6.3.3.1 Frequency tabulation of all TEAEs

6.3.3.2 Frequency tabulation of TEAEs for which the causal relationship with protocol treatment was “related”

6.3.3.3 Frequency tabulation of TEAEs for which the causal relationship with panitumumab was “related”

- 6.3.3.4 Frequency tabulation of all TEAEs by severity
- 6.3.3.5 Frequency tabulation of TEAEs by severity for which the causal relationship with protocol treatment was “related”
- 6.3.3.6 Frequency tabulation of TEAEs by severity for which the causal relationship with panitumumab was “related”
- 6.3.3.7 Frequency tabulation of TEAEs for action taken for protocol treatment was “discontinuation”
- 6.3.3.8 Frequency tabulation of TEAEs by severity for action taken for protocol treatment was “discontinuation”
- 6.3.3.9 Frequency tabulation of serious TEAEs
- 6.3.3.10 Frequency tabulation of serious TEAEs for which the causal relationship with protocol treatment was “related”
- 6.3.3.11 Frequency tabulation of serious TEAEs for which the causal relationship with panitumumab treatment was “related”
- 6.3.3.12 Frequency tabulation of non-serious TEAEs with $> 5\%$ incidence
- 6.3.3.13 Frequency tabulation of non-serious TEAEs with $> 5\%$ for which the causal relationship with protocol treatment was “related”
- 6.3.3.14 Frequency tabulation of non-serious TEAEs with $> 5\%$ for which the causal relationship with panitumumab was “related”
- 6.3.3.15 Frequency tabulation of TEAEs with \geq Grade 3
- 6.3.3.16 Frequency tabulation of TEAEs of Grade ≥ 3 for which the causal relationship with protocol treatment was “related”
- 6.3.3.17 Frequency tabulation of TEAEs of Grade ≥ 3 for which the causal relationship with panitumumab was “related”
- 6.3.3.18 The incidence rate of TEAEs of Grade ≥ 3
- 6.3.3.19 The incidence rate of TEAEs of Grade ≥ 3 for which the causal relationship with protocol treatment was “related”
- 6.3.3.20 The incidence rate of TEAEs of Grade ≥ 3 for which the causal relationship with panitumumab was “related”

The following analyses will be performed on the “set of enrolled subjects who received at least one dose of protocol treatment and satisfied all of the enrollment criteria” and the “DLT evaluation set.”

The worst grade in each subject will be calculated. The incidence rate of TEAEs of Grade ≥ 3 and the 95% confidence intervals using Agresti-Coull methods will be calculated. Similarly, incidence rate and the 95% confidence interval of TEAEs will be calculated in the number of TEAE incidence

with \geq Grade 3 as the numerator, and the TEAE collecting periods as the denominator. The 95% confidence intervals will be calculated using the following formula:

$$95\% \text{ confidence interval of incidence rate} = \text{incidence rate} \pm 1.96 \sqrt{\frac{\text{incidence rate}}{\text{TEAE collecting period}}}$$

Skin toxicity will be analyzed similarly as described above (6.3.3.1 to 6.3.3.20)

7. Statistical analysis of the phase II part of the study

7.1 Analysis set

In the phase II part of the study, statistical analysis will be performed on a “full analysis set” and “safety analysis set.” The “full analysis set” will be the main efficacy analysis set, and is defined as “subjects enrolled in phase I and II who received at least one dose of protocol treatment (RD) and satisfied all of the enrollment criteria.” RD is the recommended dose that is confirmed in the phase I part. The “safety analysis set” is defined as “subjects enrolled in phase I and II who received at least one dose of either panitumumab or TAS-102.” Additionally, the set of all subjects who are enrolled in this study is defined as “all enrolled subjects.”

The statistics representative and analysis personnel should finalize a statistical analysis plan before data fixation based on confirmation of the definition of analysis sets and appropriateness of analytical handling rules of the subject data in the analysis sets, and additional handling rules for the issues that are not determined at planning before data fixation.

7.2 Evaluation of analysis set

7.2.1 Eligibility and analysis set

A flow chart showing the breakdown of “all enrolled subjects,” “full analysis set,” and “safety analysis set,” and reasons for patients not being included in the analysis set will be tabulated and shown with a flow chart.

Reason for exclusion of safety analysis set:

- Never received panitumumab or TAS-102

Reason for exclusion of the full analysis set

- Not meeting enrollment criteria
- Never received protocol treatment (RD)

7.2.2 Analysis of demographic and other baseline characteristics

7.2.2.1 Demographic and other baseline characteristics

The following analyses will be performed on “all enrolled subjects,” the “full analysis set,” and the “safety analysis set”:

(1) Discrete data

A frequency distribution will be tabulated for discrete data, and the percentage (%) will be indicated with the analysis set as a denominator. Tabulation items are as follows:

- Age (≥ 20 to < 30 years, ≥ 30 to < 40 years, ≥ 40 to < 50 years, ≥ 50 to < 60 years, ≥ 60 to < 70 years, ≥ 70 to < 75 years; ≥ 20 to < 65 years, ≥ 65 to < 75 years), sex, information on primary organ tumor (solitary, multiple), primary tumor location [colon (cecum, ascending colon, transverse colon, descending colon, sigmoid colon), rectum (rectosigmoid, rectum)], [right side, left side], information on metastasis (number of organs with metastasis) (0, 1, ≥ 2), organs with metastasis (liver, lung, peritoneum, lymph node, bone, adrenal gland, skin, and others), ECOG Performance status (P.S.) [before treatment on Day 1 of Course 1 (0, 1)], resection of primary tumor (yes, no), adjuvant chemotherapy (yes, no), number of previous treatments (1, 2, 3), complications (absence, presence).

(2) Continuous data

Summary statistics (number of cases, the mean, standard deviation, minimum, maximum, quartiles) will be calculated for continuous data.

- Age (years), height (cm), body weight (kg) (at enrollment), BMI (kg/m^2) (at enrollment), period from the start date of first-line treatment to the date of enrollment (months) (One month is considered as 28 days in calculations).

7.2.2.2 Breakdown of complications

The frequency distribution of complications in “all enrolled subjects,” “full analysis set,” and “safety analysis set” will be tabulated, and the percentage (%) will be indicated with the analysis set as the denominator. Complications will be coded using MedDRA and summarized by SOC and PTs.

7.2.3 Medication status

7.2.3.1 Completion of administration

The summary statistics (number of cases, mean, median, standard deviation, minimum, maximum, quartiles) of the cumulative dose and relative dose intensity (RDI) up to 6 months after the start of protocol treatment (168 days) or until the completion date of the course over the period of 6 months (168 days) will be calculated by drug for the “full analysis set” and “safety analysis set.” The RDI will be calculated using the following formulae:

$$\text{Total RDI (\%)} = (\text{all actual dose/all planned dose}) \times (168/\text{actual number of days of all courses}) \times 100$$

7.2.3.2 Completion of administration by worst grade of stomatitis

The cumulative dose and summary statistics of RDI (number of cases, mean, SD, minimum, maximum, quartile) will be calculated for the “full analysis set” and “safety analysis set” by the presence/absence of stomatitis, worst grade, and by drug up to 6 months (168 days) after the start of protocol treatment or to the date of completion of the course across 6 months (168 days).

7.2.3.3 Initial onset of stomatitis and cumulative dose

Kaplan-Meier method will be used to estimate survival curve until the onset of event in the “safety analysis set,” and the point estimation value of incidence and its 95% confidence interval (two-sided) will be calculated at the quartile of the cumulative dose to the initial onset of event and specified time points.

Cumulative dose is to be the dose accumulated by the time of initial onset of event for each drug. For cases without event occurrence, the cumulative dose to the date of death, date of discontinuation/dropout, date of last survival confirmation, or the date of data cut-off, whichever is earlier, will be used.

First onset of event: \geq Grade 1 stomatitis, \geq Grade 2 stomatitis, \geq Grade 3 stomatitis

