8.1 Definition of protocol treatment

With protocol treatment in principle, combination therapy with panitumumab and TAS-102 stipulated in the “8.2 treatment regimen” will be conducted, and even if any of the criteria for suspension or discontinuation of each drug is met, treatment with other drugs will be continued unless any of the criteria for discontinuation of protocol treatment is met (such as in case of PD).

Protocol treatment in principle will be initiated within 14 days of entry.

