8.7 Criteria for discontinuation of protocol treatment for each subject

The number of doses is not specified. However, protocol treatment should be discontinued when any of the criteria for discontinuation of protocol treatment listed below is met. The date of discontinuation of protocol treatment is defined as the date when the investigator or the subinvestigator decides on discontinuation of protocol treatment. The investigator or the subinvestigator should record the main reason for discontinuation of protocol treatment in the case report form (hereinafter referred to as CRF) according to the classification described below. For subjects discontinuing before enrollment, see 9.3 Records of subjects who discontinued before enrollment.

1. Lack of efficacy (exacerbation)

When PD is evident in the clinical or imaging evaluation

2. Adverse event

Discontinuation of treatment due to an adverse event in the opinion of the investigator or the subinvestigator, or according to the protocol treatment discontinuation criteria. However, death during protocol treatment will be classified in “4. Death during protocol treatment” and not in this item.

Protocol treatment is postponed due to adverse event for 58 days or more after the day of starting the last course. However, postponement due to holidays is allowed.

3. Voluntary discontinuation

A subject wishes to discontinue study participation. The reason for discontinuation should be recorded in CRF when it is clarified.

CONFIDENTIAL

Note: Attempts should be made as best as possible to clarify the reason for voluntary discontinuation. (Discontinuation due to adverse event or lack of efficacy should not be classified as “voluntary discontinuation”).

4. Death during protocol treatment

Death before discontinuation of protocol treatment is decided. Date of death, reason of death (protocol treatment related, primary disease, others) should be described in the CRF.

5. Significant deviation from the protocol

When study continuation may cause intolerable risk to the health of a subject because the subject was found not to satisfy the inclusion criteria specified in the protocol after enrollment or the protocol has not been observed.

6. Lost to follow-up

When subject fails to make visits and cannot be contacted. The attempts that were made to contact the subject should be recorded in the source documents.

7. Discontinuation of the entire study

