10.2 Procedures

10.2.1 Collection and reporting of adverse events

10.2.1.1 Period for collection of adverse events

Adverse events should be continuously collected from initiation of protocol treatment up to 4 weeks (28 days) after discontinuation of protocol treatment or initiation of follow-up treatment, whichever date is earlier. In addition, adverse event causal relationship cannot be ruled out of protocol treatment collected later 4 weeks (28 days) after discontinuation of protocol treatment or initiation of follow-up treatment.

CONFIDENTIAL

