7.2.4.4 Other efficacy analysis items

1) ETS

The presence/absence of cases with tumor shrinkage by at least 20% within 8 weeks after enrollment, the number of patients who dropped out (discontinued protocol treatment) within 8 weeks after enrollment in the full analysis set, and the dropout rate will be shown.

2) Administration of each drug and the change from the onset of response to death or completion of observation

Swimmers plot will be created to illustrate the change from the onset of response to death or completion of observation.

Date of response onset: the date CR or PR is first confirmed

Vertical axis: case

Horizontal axis: duration (days)

Administration status: A bar graph showing the duration of TAS administration (from Day 1 of TAS-102 to the date of last administration of TAS-102, with “x” indicating administration of panitumumab.

▲ will indicate the date of discontinuation of protocol treatment.

Therapeutic effect: ○ will indicate the date of response onset

■ will indicate the confirmation date of PD.

Survival: The OS part after discontinuation of protocol treatment will be indicated as ---- (survivors will be distinguished by color)

Post treatment: ● will indicate the start date of post treatment.

3) Time-course change in the reduction rate of the sum of target lesion diameters

A spider plot will be created to describe the reduction rate of the sum of target lesion diameters in all patients by best overall response of PR, SD, and PD.

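### SAP v4.0 section 7.2.3.3 labels a Kaplan-Meier estimate as stomatitis incidence while censoring at death and discontinuation; read as the share of treated subjects affected, it is biased upward

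*SAP*

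**What the plan says.** Section 7.2.3.3 of SAP v4.0 sits under Medication status and applies to the safety analysis set. Its method: "Kaplan-Meier method will be used to estimate survival curve until the onset of event in the" set named there, with cumulative dose of each drug as the axis. Three events are analysed: first stomatitis of Grade 1 or higher, Grade 2 or higher, and Grade 3 or higher. The output is stated as "the point estimation value of incidence and its 95% confidence interval (two-sided) will be calculated at the quartile of the cumulative dose" and at specified points.

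For subjects who never have the event: "For cases without event occurrence, the cumulative dose to the date of death, date of discontinuation/dropout, date of last survival confirmation" or data cut-off, whichever is earliest. The word censored does not appear, but with a Kaplan-Meier estimator this is what the rule does. The section does not say whether discontinuation means stopping that drug or stopping protocol treatment. Elsewhere (7.2.4.4) the SAP glosses dropout in its count of "the number of patients who dropped out (discontinued protocol treatment) within 8 weeks after enrollment". No competing-risk method is named anywhere in the SAP.

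Three protocol provisions bear on this. Progression ends protocol treatment (8.7: "When PD is evident in the clinical or imaging evaluation"). If one drug is stopped, "treatment with other drugs will be continued unless any of the criteria for discontinuation of protocol treatment is met" (8.1). And adverse events are still recorded after treatment ends: "Adverse events should be continuously collected from initiation of protocol treatment up to 4 weeks (28 days) after discontinuation of protocol treatment", or until follow-up treatment starts if that is earlier (10.2.1.1).

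**The concern.** On a cumulative-dose axis, a subject who dies or permanently stops a drug gains no more of it, so a first stomatitis at a higher dose of that drug cannot occur. Death and discontinuation are therefore competing events for the question of how many treated subjects develop stomatitis by a given dose. Censoring them treats these subjects as if they would have gone on to develop stomatitis at the rate seen in those still being dosed. The curve then estimates risk had nobody stopped or died, yet it is labelled incidence.

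The affected group is probably large, because progression ends treatment and the design assumes only 48% progression-free at 6 months. Stomatitis matters because protocol section 4.2 singles it out as the toxicity the two drugs share. The report would carry a Kaplan-Meier incidence here and a lower crude proportion in the 7.2.5 tables for the same event, with nothing to explain the difference.

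**Working it through.** The documents state no figure for this quantity, so there is none to reproduce. The check compares 1 minus Kaplan-Meier with the true cumulative incidence in a two-cause hazard model.

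**Inputs from the documents**
- Expected progression-free rate at 6 months 48%, threshold 29% (protocol 6.2.2.2).
- Any-grade stomatitis: TAS-102 alone 15.1% and panitumumab alone 9.8% (Table 4.f); panitumumab alone 23% (Table 4.b).
- Grade 3 or higher: none listed for TAS-102 (Table 4.d), 0 for panitumumab alone (Table 4.b), 9% (Grade 3/4) with panitumumab plus FOLFOX4 (Table 4.a).

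**Assumptions**
- The progression-free rate stands in for the share still on treatment at six courses, and dose accrues in proportion to courses.
- Any-grade incidence on the combination is 15.1%, or the single-agent rates combined as independent: 1 − (1 − 0.151)(1 − 0.098) = 23.4%, and 1 − (1 − 0.151)(1 − 0.23) = 34.6%.
- A 5% rate illustrates Grade 3 or higher.

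**Formulas**, with L the stomatitis hazard and M the hazard of stopping or dying, per course, and T = 6:
- M = −ln(S)/T, where S is the share still on treatment.
- Constant hazard: true incidence = L/(L+M) × (1 − exp(−(L+M)T)); 1 − KM = 1 − exp(−LT).
- Front-loaded: cumulative stomatitis hazard H(t) = a√(t/6) (Weibull shape 0.5); true incidence = ∫ h(t) exp(−H(t) − Mt) dt over 0 to 6, where h is the derivative of H; 1 − KM = 1 − exp(−a).
- All onset in the first two courses: the constant-hazard formulas with T = 2 and M unchanged.

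In each case L or a is solved so that the true incidence equals the assumed value.

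**Worked example** (S = 48%, true incidence 23.4%, constant hazard)
- M = −ln(0.48)/6 = 0.1223.
- L = 0.0649, because 0.0649/0.1872 × (1 − exp(−6 × 0.1872)) = 0.347 × 0.675 = 0.234.
- 1 − KM = 1 − exp(−6 × 0.0649) ≈ 32.3%, an excess of 8.9 points.

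**Excess of 1 − KM over the true incidence at six courses, in percentage points**

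| Still on treatment | True incidence | Constant hazard | Front-loaded | All in first two courses |
|---|---|---|---|---|
| 48% | 5% | 2.0 | 1.2 | 0.6 |
| 48% | 15.1% | 5.9 | 3.5 | 1.9 |
| 48% | 23.4% | 8.9 | 5.3 | 2.8 |
| 48% | 34.6% | 12.4 | 7.3 | 4.0 |
| 29% | 5% | 3.6 | 2.0 | 1.1 |
| 29% | 15.1% | 10.5 | 5.9 | 3.2 |
| 29% | 23.4% | 15.5 | 8.7 | 4.8 |
| 29% | 34.6% | 21.1 | 11.9 | 6.9 |

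For scale, the standard error of a proportion of 23.4% in 52 subjects is √(0.234 × 0.766/52) = 5.9 points. At 48% on treatment the constant-hazard excess (8.9) exceeds it, and the excess with all onset in two courses (2.8) is under half of it.

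The sign is the same in every cell. The size depends on three things the documents do not supply: the stomatitis rate, its timing and the discontinuation rate. The table is for the end of a six-course horizon; the excess is smaller at lower doses.

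**The case against.** The strongest defence is that Kaplan-Meier answers a sensible question. In a section about medication status, on a dose axis, one may want to know how risk builds while dosing continues. If censoring is independent, Kaplan-Meier estimates that, whereas a cumulative incidence function falls when progression is faster and so mixes toxicity with efficacy. This stands as far as it goes: Kaplan-Meier is not wrong in itself. But the SAP does not state that estimand; it calls the result incidence. Independence is also doubtful for the Grade 3 or higher curve. Table 8.e requires most non-hematological toxicity to be Grade 1 or lower before a TAS-102 course starts, and section 8.5.2 ends TAS-102 after more than 28 days without administration. Persistent Grade 2 stomatitis could therefore itself lead to censoring.

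A second defence is that little hangs on it. Crude frequencies by severity (7.2.5), days to onset (7.2.6.3), and dose and dose intensity by stomatitis grade (7.2.3.2) are all planned. A reader might infer that 7.2.3.3 is the only planned account of when stomatitis appears; it is not. This defence limits the weight of the point but leaves the label wrong.

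A reader might also infer that discontinuation makes the event impossible. That is too strong. Adverse events are collected for up to 28 days afterwards, and a subject who stops one drug may stay on the other. Such events can be recorded, but only at the dose of the stopped drug already reached.

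**Conclusion.** The point holds as a labelling and estimand fault in a supplementary descriptive analysis. Read as the share of treated subjects with stomatitis, the planned estimate is biased upward in every scenario tested.

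It is tempting to attach one figure to this, such as 5 to 12 points. The documents do not support that. Such a range describes any-grade stomatitis under particular onset patterns with 48% still on treatment, and it cannot apply alike to all three grade thresholds. Both the combination's stomatitis rate and the use of the progression-free rate for treatment continuation are assumed.

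The primary endpoint, the secondary efficacy endpoints and the dose decision are unaffected. Ending follow-up at last survival confirmation or data cut-off is ordinary censoring and is not in question. The amendment is still worth making, because the reported number changes and the correction is cheap.

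**What to change.** In 7.2.3.3, take the point incidences and 95% confidence intervals from the cumulative incidence function (Aalen-Johansen) over cumulative dose. Treat death and permanent discontinuation of the drug before stomatitis as competing events, and censor only subjects still on that drug at data cut-off. Naming the drug also settles what discontinuation means in this section.

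State that stomatitis recorded after a drug is stopped, whether within the 28-day window or while the other drug continues, counts as an event at the cumulative dose of the stopped drug already reached.

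If the Kaplan-Meier curve and its dose quartiles are kept, label them as risk while dosing continues, not incidence.

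The cost is a short SAP edit and a standard procedure, with no new data. The downside is that dose quartiles from the cumulative incidence function may not be reached: at a true incidence of 23.4% not even the 25% point is attained, and at 34.6% the median is not.

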7.2.3.4 Reason for discontinuation of protocol treatment

Reasons for discontinuation of patients who withdraw up to 6 months (168 days) and during the entire study period in the “full analysis set” and “safety analysis set” will be tabulated, and the percentage (%) will be indicated with the respective analysis set as the denominator.

Reasons for discontinuation of protocol treatment:

- Lack of efficacy (progression)
- Adverse event
- Voluntary discontinuation
- Death during protocol treatment
- Significant deviation from the protocol
- Lost to follow-up
- Discontinuation of the entire study
- Pregnancy
- Others

7.2.3.5 Dose reduction status

The frequency and percentage (%) of the subjects with dose reduction from the initial dose of the treatment period up to 6 months after the start of protocol treatment (168 days), or until the completion date of the course over the period of 6 months (168 days), and over the entire study period will be tabulated for each drug for the “full analysis set” and “safety analysis set.” Drug withdrawal or treatment discontinuation will not be regarded as dose reduction.

7.2.3.6 Follow-up status

The quartiles of follow-up period will be calculated in the “full analysis set” and “safety analysis set.” The follow-up period is the period from the day of enrollment until the day of completion of follow-up. The reverse Kaplan-Meier method will be used to calculate the quartiles of the follow-up period.¹⁾ The final date of follow-up is the date before the date of death for the case of death, and on the final day on which survival is confirmed for surviving subjects

